### 9.5.1.3.3 Laboratory Measurements

Laboratory tests to be performed according to the guideline of each site. In case that laboratory test is performed, laboratory abnormality may meet the criteria to qualify as an AE as described in this protocol (see Section 9.5.1.3.1). In these instances, the AE corresponding to the laboratory abnormality will be recorded on the Adverse Event CRF.

Category	Parameters
Hematology	hematocrit, hemoglobin, platelets, RBC count, and WBC count with differential (bands, basophils, eosinophils, lymphocytes, monocytes, neutrophils)
Chemistry	Na, K, Ca, Cl, CPK, BUN, Creatinine, Uric acid, Total bilirubin, Albumin, Total protein, ALT, AST, $\gamma$ -GTP, Alkaline phosphatase
Urinalysis	Specific gravity, pH, Protein, Glucose, Bilirubin, Ketones, RBC, WBC, Creatinine

### 9.5.1.3.4 Vital Signs and Weight Measurements

Vital sign measurements (i.e., systolic and diastolic blood pressure [mmHg], pulse [beats per minute], body temperature [in centigrade]), and weight (kg) will be obtained at the visits designated in Table 3 by a validated method.

Vital signs will include blood pressure, pulse, and body temperature. Blood pressure and pulse will be measured after the subject has been sitting for 5 minutes. All blood pressure measurements should be performed on the same arm, preferably by the same person.

Documentation of vital signs will be included in the source documentation at the site. Clinically significant abnormal findings at Visit 1 (Screening) will be recorded on the medical history CRF. Only changes from screening vital signs findings that meet the definition of an AE will be recorded on the Adverse Event CRF.

### 9.5.1.3.5 Physical Examinations

Physical examinations will be performed as designated in Table 3. Documentation of the physical examination will be included in the source documentation at the site. Clinically significant abnormal findings at Visit 1 (Screening) will be recorded on the medical history CRF. Only changes from screening physical examination findings that meet the definition of an AE will be recorded on the Adverse Event CRF.

### 9.5.1.3.6 Electrocardiograms

ECG will be performed as designated in Table 3. An ECG abnormality may meet the criteria of an AE as described in this protocol (see Section 9.5.1.3.1). In these instances, the AE corresponding to the ECG abnormality will be recorded on the Adverse Event CRF.

## **9.5.2 Schedule of Procedures/Assessments**

### **9.5.2.1 Schedule of Procedures/Assessments**

Table 3 presents the schedule of procedures/assessments for this study.

**Table 3. Schedule of Procedures/Assessments in Study ME2125-M082-401**

Visit	Visit 1	Visit 2	Visit 3	Visit 4 (EOT)	Visit 5	Premature Discontinuation Visit c
Period	Screening Period	Baseline	Treatment Period a		Taper Period b	
Week	-3 weeks to -1 day	0	8 weeks	18 weeks	19 weeks	
Visit window	0	0	- 4 weeks / + 2 weeks	± 2 weeks	±1 week	
Informed Consent	x					
Eligibility Assessment	x	x				
Demography d	x					
Height	x					
Weight	x	(x)	(x)	x	(x)	x
Medical History e	x					
Prior and Concomitant Medications/ Concomitant Therapies f	x	x	x	x	x	x
Clinical Laboratory Tests g	x		(x)	x	(x)	x
12-lead ECG h	(x)		(x)	(x)	(x)	(x)
Vital Signs i	x	x	x	x	x	x
Urine Pregnancy Test j	x			x		x
Physical Examinations	x	x	x	x	x	x
Dispense study drug k		x	x	x*		x*
Study drug administration l		→			x	

Visit	Visit 1	Visit 2	Visit 3	Visit 4 (EOT)	Visit 5	Premature Discontinuation Visit c
Period	Screening Period	Baseline	Treatment Period a		Taper Period b	
Week	-3 weeks to -1 day	0	8 weeks	18 weeks	19 weeks	
Visit window	0	0	- 4 weeks / + 2 weeks	± 2 weeks	±1 week	
Retrieve unused study drug			x	x	x	x
Check study drug compliance			x	x	x	x
AE assessment m	→				x	x
Efficacy assessment						
Review of Subject diary Card n : Daily “off” time and “on” time	x *	x		x		x
PDQ-39		x		x		x
MDS-UPDRS Part 3		x		x		x
MDS-UPDRS Part 4		x		x		x
KPPS		x		x		x
MMSE	x o			x		x

12-lead ECG, Electrocardiogram; EOT, End of Treatment; KPPS, King’s Parkinson’s disease Pain Scale; MMSE, Mini-Mental State Examination; MDS-UPDRS, Movement Disorder Society-Unified Parkinson’s Disease Rating Scale; PDQ-39, Parkinson’s Disease Questionnaire-39

- a Regular site visits will be determined by the treating investigators according to standard clinical practice as long as visits are made within the visit window
- b Subjects who complete 18 weeks of treatment may undergo a Taper Period for 1 week if necessary. The Taper Period may be omitted if the subject’s daily dose of study drug at the end of treatment is 50mg, if subjects will continue to take the study drug after the completion of the trial, or if it is considered not required by an investigator.  
For the subjects who do not require the Taper Period, their participation in the study will be completed after the completion of Visit 4 (EOT)
- c A subject who prematurely discontinues taking the study drug should return to the site as soon as practicable after discontinuing study drug (preferably within 7 days) to complete Premature Discontinuation Visit. Following the completion of Premature Discontinuation Visit, the subjects who require taper will undergo a Taper Period for 1 week
- d Demography information includes year and month of birth (age) and sex
- e All medical history within 6 months and surgical history within 3 years will be recorded in the medical history CRF
- f Prior medication within 1 month and current medications (including levodopa) will be recorded at Visit 1 (Screening).  
The information on prior medication will include the name of the product or ingredient, dose and administration (daily dose and dose unit), administration period (start date and end date), and purpose of administration

- Any concomitant medications and therapies during this study (starting at the date of informed consent) will be recorded at each visit. The information on concomitant medications (including levodopa) will include the name of product or ingredient, dose and administration (daily dose and dose unit), administration period (start date and end date), and purpose of administration. The information on concomitant therapies should include the name of therapy, therapy period (start date and end date), and purpose of therapy. Any Adverse Events or medical status shall be recorded during the administration of concomitant medication or use of concomitant therapy.
- g Clinical laboratory tests to be performed according to the guideline of each site
- At Visit 3 and Visit 5, clinical laboratory tests will only be performed if considered necessary by an investigator based on the subject's symptoms
- In case of tests related to liver function, a re-test or re-screening is allowed once during the Screening period
- h ECG will only be performed if considered necessary by an investigator based on the subject's symptoms
- i Vital signs will include blood pressure, pulse, and body temperature. Vital signs will be measured preferably after the subject has rested comfortably for 5 minutes at each visit
- j Females of childbearing potential only. A dipstick will be used for urine pregnancy testing
- k Subjects will administer the study drug at the dose prescribed at regular visits from the next day after that visit to the day of the next regular visit
- \*It is not necessary to distribute the study drug at Visit 4 (EOT) or Premature Discontinuation Visit to subjects who do not proceed with the tapering period
- l Study drug will be distributed to subjects who continue to meet the eligibility criteria at Visit 2 (baseline), and they are instructed to take the study drug daily for the next 18 weeks from the next day after Visit 2 (baseline). The dose of the study drug is started at 50 mg once a day for 2 weeks (14 days) starting from the next day after Visit 2 (Baseline) and is increased to 100 mg once a day afterwards. Subjects who need to increase the dose at the discretion of an investigator shall visit the site (unscheduled) prior to the dose increase. If an Adverse Event occurs following the increase in dose, the investigator may reduce the dose back to 50 mg/day through unscheduled site visit or phone visit. After reduction from 100mg/day to 50mg/day, the dose may be increased back to 100 mg/day at the discretion of the investigator
- m All adverse events (AEs) should be recorded after Visit 1 (Screening) to the last visit, regardless of relevance to the study drug or the procedure, and all AEs should be followed up until the end of the study (subject's last visit). During the AE evaluation, events associated with special situations listed in Section 9.5.4.2 are also evaluated
- All serious adverse events (SAEs) should be followed up until resolution or, if no resolution is possible, until stabilization
- n At Visit 2 (Baseline) and Visit 4 (EOT), the investigators will review the completed subject diary with subjects. Subjects must complete the diary at least three consecutive days prior to each visit where completed diary review is conducted (Visit 2, Visit 4). At Visit 4 (EOT), subjects shall submit the diary to the investigators or other clinical trial staff
- \* Subjects and/or their caregivers will receive a subject diary and investigator will train them how to complete the diary at Visit 1 (Screening). Subjects who meet the eligibility criteria of the study will be instructed to complete the diary for 3 consecutive days prior to Visit 2 (Baseline)
- o The result from MMSE conducted at Visit 1 (Screening) will be the baseline result. If MMSE was not conducted at Visit 1 (Screening), it can be performed at Visit 2 (Baseline) and then the MMSE result from Visit 2 (Baseline) will be considered as baseline result. In other words, if MMSE is conducted at either Visit 1 (Screening) or Visit 2 (Baseline), the subject will be considered to have completed the MMSE

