## 2 CLINICAL PROTOCOL SYNOPSIS

Compound No.: ME2125
Name of Active Ingredient: safinamide mesilate
Study Protocol Title A multi-center, open-label phase 4 study evaluating the efficacy and safety of safinamide mesilate as add-on therapy to levodopa in Parkinson's Disease patients with motor fluctuation in South Korea
Sites Approximately 20 sites
Study Period and Phase of Development Approximately 13 months (may be shortened or extended depending on registration status) Phase 4
Objectives Primary Objective To evaluate the change at the 18th week from baseline in daily "off" time measured by subject diary and Parkinson's Disease Questionnaire-39 (PDQ-39) in patients with Parkinson's Disease who are receiving levodopa.  Secondary Objective 

• To evaluate the change at the 18th week from baseline in below assessments:

- Movement Disorder Society-Unified Parkinson's Disease Rating (MDS-UPDRS) Part 3

- Movement Disorder Society-Unified Parkinson's Disease Rating (MDS-UPDRS) Part 4

- King's Parkinson's disease Pain Scale (KPPS)

- Mini-Mental State Examination (MMSE)

• To evaluate the safety of safinamide mesilate in Parkinson's Disease patients who are receiving levodopa

• To evaluate the change at the 18th week from baseline in daily "on" time without dyskinesia in patients with Parkinson's Disease who are receiving levodopa

Study Design This is a multi-center, open-label, single-arm, interventional study in Parkinson's Disease patients who are receiving levodopa. After providing written informed consent, subjects will enter the Screening Period for maximum 21 days and then Baseline Period for 1 day. If subjects are eligible, Treatment Period will begin in which subjects will be treated with safinamide mesilate (hereinafter, study drug) for 18 weeks.  After the Treatment Period, subjects' participation in the study will be completed after the completion of Visit 4 (EOT), which is the End of Treatment Visit. At Visit 4(EOT), the subjects who require tapering will enter a Taper Period for 1 week. The Taper Period may be omitted if the subject's daily dose of study drug at the end of treatment is 50mg, if subjects will continue to take the study drug after the completion of the trial, or if it is considered not required by an investigator.

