**[Baseline Period]**

At Visit 2 (Baseline), subjects will return to the site after they have completed the diary for at least 3 consecutive days. At Visit 2 (Baseline), safety assessments including AE assessment, vital signs, weight (if deemed necessary by an investigator), and physical examination will be conducted.

Efficacy assessments including Parkinson's Disease Questionnaire-39 (PDQ-39), Movement Disorder Society-Unified Parkinson's Disease Rating Scale (MDS-UPDRS) Part 3 and Part 4, and King's Parkinson's disease Pain Scale (KPPS) will be conducted. Investigators will also review the completed subject diary with subjects.

The study drug will be distributed to the subjects who meet the eligibility criteria at Visit 2 (Baseline). Subjects will be instructed to take the study drug every day starting from the day after Visit 2 (Baseline).

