### **9.1.1 Screening Period**

The purpose of the Screening Period is to obtain informed consent and to establish protocol eligibility. Informed consent will be obtained after the study has been fully explained to each subject and before the conduct of any screening procedures or assessments. Procedures to be followed when obtaining informed consent are detailed in Section 5.3.

Subjects must have a diagnosis of Parkinson's Disease and receive levodopa at a stable dose for at least 4 weeks prior to the screening visit. After signed informed consent is obtained from the subject or for subjects from Legally Acceptable Representatives (LARs), a medical history interview, identification of prior and concomitant medications, identification of concomitant therapies, height, weight, physical examination, urine pregnancy test (females of childbearing potential only), 12-lead electrocardiogram (ECG; if deemed necessary by an investigator), vital signs, clinical laboratory tests (hematology, chemistry, and urinalysis), and Adverse Events (AE) assessment will be conducted for evaluation of eligibility criteria, and will include confirmation that the subject meets diagnostic criteria for Parkinson's Disease.

At Visit 1 (Screening), subjects will perform the Mini-Mental State Examination (MMSE) among the efficacy assessments. Also, a diary will be handed out to subjects and/or their caregivers, and investigator will train them how to complete the diary. Subjects who meet the eligibility criteria of the study will be instructed to complete the diary for 3 consecutive days prior to Visit 2 (Baseline).

If subjects have previously taken medication such as COMT inhibitor and/or MAO-B inhibitor, they have to undergo an appropriate wash-out period for each medication (3 days for COMT inhibitor; 14 days for MAO-B inhibitor).

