### 9.3.2 Exclusion Criteria

To be eligible for inclusion into this trial, the subjects must not meet any of the following criteria:

1. Females who are planning for pregnancy, pregnant or breastfeeding
2. Prior use of safinamide
3. If patients have previously taken medication such as COMT inhibitor and/or MAO-B inhibitor, they have to take appropriate wash-out period for each medication.(3 days for COMT inhibitor; 14 days for MAO-B inhibitor)
4. Use of medications for depression or psychosis within 5 weeks prior to Screening Visit
5. History of allergic response to levodopa, or other anti-Parkinsonian agent
6. Hypersensitivity or contraindications to MAO-B inhibitors
7. Confirmed ophthalmologic history including any of the following conditions: albino subjects, family history of hereditary retinal disease, progressive and/or severe diminution of visual acuity (i.e., 20/70 on Snellen Chart), retinitis pigmentosa, retinal pigmentation due to any cause, any active retinopathy or ocular inflammation (uveitis), or diabetic retinopathy.
8. Patients who did not consent to having at least 7 days of washout period prior to Visit 2, if known to take narcotic analgesics 7 days prior to Screening Visit (eg, pethidine hydrochloride-containing products, tramadol hydrochloride, or tapentadol hydrochloride)
9. History of serotonergic medications administration (eg, tricyclic antidepressants, tetracyclic antidepressants, selective serotonin reuptake inhibitors, serotonin–noradrenaline reuptake inhibitors, selective noradrenaline reuptake inhibitor, or noradrenergic and serotonergic antidepressant) within 5 weeks prior to the Screening Visit
10. Administering central nervous system stimulants (eg, methylphenidate hydrochloride, lisdexamfetamine mesilate)
11. Administering dextromethorphan
12. Patients with clinically significant liver function abnormalities defined as > 1.5 times of the upper limit of the normal range of total bilirubin or > 3 times of the upper limit of the normal range of ALT or AST; re-examination and re-screening are allowed once within the screening period
13. Have a history of hypersensitivity to any of the ingredients of the product
14. Currently enrolled in another clinical trial or used any investigational drug/biologics or device within 30 days or 5 × the half-life, whichever is longer, preceding informed consent

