**9.5.2.2.2 Visit 2 (Baseline, 0 week)**

At Visit 2 (Baseline), the following procedures will be performed:

- Reconfirmation of eligibility assessment
- Weight: if deemed necessary by an investigator
- Concomitant medications
- Concomitant therapies
- Vital signs
- Physical examinations
- Study drug dispensation
- AE assessment
- Efficacy assessments including PDQ-39, MDS-UPDRS Part 3 and Part 4, and KPPS, are performed. The completed subject diary will be reviewed by an investigator together with a subject.

If MMSE was not conducted at Visit 1 (Screening), it can be performed at Visit 2 (Baseline). If MMSE is conducted at either Visit 1 (Screening) or Visit 2 (Baseline), the subject will be considered to have completed the MMSE.

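### No urine pregnancy test at Visit 2: the only scheduled pre-dose test is a Screening dipstick about 4 to 22 days old at first dose (low severity, cheap to improve)

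*Combined protocol and SAP*

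**What the plan says.** Table 3 in Section 9.5.2.1 has a row "Urine Pregnancy Test" marked at Visit 1, Visit 4 (EOT) and the Premature Discontinuation Visit. The Visit 2, 3 and 5 cells are blank. Note j limits the test to females of childbearing potential and names a dipstick as the method. The visit descriptions agree: the test is listed in Sections 9.5.2.2.1 (Visit 1) and 9.5.2.2.4 (Visit 4), and not in 9.5.2.2.2 (Visit 2) or 9.5.2.2.3 (Visit 3). The Baseline Period text in the synopsis and in Section 9.1.2 says that at Visit 2 "safety assessments including AE assessment, vital signs, weight (if deemed necessary by an investigator), and physical examination will be conducted", again without a pregnancy test.

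The first exclusion criterion in Section 9.3.2 is "Females who are planning for pregnancy, pregnant or breastfeeding". The Visit 2 list in Section 9.5.2.2.2 opens with "Reconfirmation of eligibility assessment", and Table 3 note l adds: "Study drug will be distributed to subjects who continue to meet the eligibility criteria at Visit 2 (baseline"). Section 9.1.3 likewise lets only subjects who still satisfy all criteria enter the Treatment Period.

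On timing, the synopsis says "subjects will enter the Screening Period for maximum 21 days". At Visit 1 "a diary will be handed out to subjects and/or their caregivers" (Section 9.1.1), and note n states "Subjects must complete the diary at least three consecutive days prior to each visit where completed diary review is conducted". Under Section 9.1.2, dosing begins the day after Visit 2.

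**The concern.** Exclusion 1 has to be clear when drug is dispensed, but the only scheduled objective evidence behind it was collected at Screening. Unlike a fixed item of history, pregnancy status can change during that interval. Two kinds of case could pass the Visit 2 check: a conception between Visit 1 and Visit 2, and a conception shortly before Visit 1 that the first dipstick was too early to show. Either would lead to exposure of a subject whom exclusion 1 is meant to keep out.

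For a subject who stays on treatment, the next scheduled test is at Visit 4. A pregnancy missed at Visit 2 could therefore go through most or all of the Treatment Period without meeting a scheduled test.

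What is at stake is safety before first dose. The primary and secondary efficacy analyses and the sample size are untouched.

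**Working it through.** The plan gives no figure for the age of the test at first dose, so there is none to reproduce. The check is calendar arithmetic.

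**Inputs**

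- Visit 2 is day 0 and first dose is day +1 (Section 9.1.2).
- Screening lasts at most 21 days, so the earliest Visit 1 is day −21 (synopsis, Study Design; Table 3).
- The diary is issued and taught at Visit 1, and at least 3 consecutive days must be completed before Visit 2 (Section 9.1.1; Table 3 note n). The latest workable Visit 1 is therefore day −3. It would be day −4 if the diary starts the day after Visit 1. Table 3 nominally allows Visit 1 as late as day −1, but the diary rule excludes that.
- Wash-out before Visit 2 is 14 days for an MAO-B inhibitor and 3 days for a COMT inhibitor (Sections 9.1 and 9.1.1).
- Visit 4 falls at week 18 ± 2 (Table 3).

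**Formula:** age of test at first dose = (+1) − (day of Visit 1).

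| Situation | Day of Visit 1 | Age at first dose |
|---|---|---|
| Longest Screening | −21 | 1 + 21 = 22 days |
| Shortest Screening, diary starts at Visit 1 | −3 | 1 + 3 = 4 days |
| Shortest Screening, diary starts the next day | −4 | 1 + 4 = 5 days |
| MAO-B wash-out begun at Visit 1, shortest | −14 | 1 + 14 = 15 days |
| Test repeated at Visit 2 | – | 1 − 0 = 1 day |

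The range is therefore about 4 to 22 days, and 15 to 22 days for a subject who stops an MAO-B inhibitor at Visit 1. A 3-day COMT wash-out leaves the lower end at 4. The one permitted liver re-test or re-screening must fall within the Screening Period, so it does not extend the upper end.

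**Interval to the next scheduled test:** Visit 4 at week 16 to 20 is 16 × 7 = 112 to 20 × 7 = 140 days after Visit 2. This holds with or without a Visit 2 test.

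**Women affected.** The documents give no number. Taking shares of 0%, 1%, 5% and 10% of 199 subjects as an assumption: 199 × 0 = 0; 199 × 0.01 ≈ 2; 199 × 0.05 ≈ 10; 199 × 0.10 ≈ 20.

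**Other controls before or soon after first dose**

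- Exclusion 1 also bars women planning pregnancy. That does not cover an unplanned one.
- Pregnancy is one of the special situations considered at each AE assessment (Table 3 note m; Section 9.5.4.2). That depends on the pregnancy being known.
- An unscheduled visit may precede the increase to 100 mg (Section 9.5.2.2.6). It comes after dosing has begun, is conditional, and lists no pregnancy test.

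None of these is designed to find a pregnancy that the subject has not recognised.

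**The case against.** The strongest reply is that this is a preference. The protocol sets a Screening window and accepts Visit 1 results within it. The clinical laboratory tests, including the liver tests behind exclusion 12, are also done at Visit 1 and left blank at Visit 2. Nothing in the documents requires a pregnancy test within a given number of days of dosing. Section 9.5.4.2.1 already governs a pregnancy once it is known: reporting within 24 hours, follow-up to outcome, and withdrawal unless benefit is judged to outweigh risk and the subject consents. An investigator may also test at Visit 2 without being told to.

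The benefit can also be questioned. It is expressed as the age of a test and not as a risk, because the documents give no conception rate, no dipstick sensitivity and no number of women. A conception after Visit 1 is at most 21 days old at Visit 2, which is where a dipstick may miss it. The longer interval, 112 to 140 days on treatment, is unchanged.

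Much of this stands. There is no contradiction and no breached requirement, the gain is small and unquantified, and it is smallest when Screening is short. Two parts do not carry. Section 9.5.4.2.1 acts after a pregnancy is recognised and does not detect one before dosing. And the Visit 2 test is not confined to conceptions after Visit 1: one that was too early to show at Visit 1 is 3 to 21 days further on by Visit 2.

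**Conclusion.** The concern holds as a low-severity, optional improvement. The last scheduled pregnancy test before first dose is about 4 to 22 days old, or 15 to 22 days with an MAO-B inhibitor wash-out started at Visit 1. Eligibility is nevertheless meant to be current when drug is dispensed.

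The upper end follows directly from the stated 21-day maximum and next-day dosing. The lower end is derived from the diary rule and would be 5 days on the stricter reading. The figure of 0 to about 20 women rests wholly on the assumed 0% to 10% share, and the true number may be very small. The risk of an exposed pregnancy cannot be computed from the documents. No efficacy conclusion changes.

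**What to change.** Schedule the urine pregnancy test at Visit 2 for females of childbearing potential:

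- mark the Visit 2 cell in Table 3;
- add the test to the Visit 2 list in Section 9.5.2.2.2;
- add it to the Visit 2 safety assessments in the synopsis (Baseline Period) and in Section 9.1.2;
- add to note j: *At Visit 2, a negative result is required before study drug is dispensed.*

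This brings the age of the last scheduled test at first dose down to 1 day. A dipstick can still miss a very early pregnancy, so the risk is reduced and not removed.

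The running cost is one dipstick per woman at a visit she already attends, by the method already in use: 0 to about 20 dipsticks under the assumption above. The administrative cost is short edits in five places and an amendment resubmitted to the IRB/IEC (Section 5.1) across about 20 sites (Section 6). Combining it with another amendment avoids a separate submission. The documents do not mention one, though, and the change helps only subjects who have not yet been dispensed drug, so a long wait would use up the benefit.

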## 9 INVESTIGATIONAL PLAN

### 9.1 Overall Study Design and Plan

This is a multi-center, open-label, single-arm, interventional study in Parkinson's Disease patients who are receiving levodopa. Approximately 199 patients will be enrolled and will receive safinamide mesilate (hereinafter, study drug) for approximately 18 weeks (Figure 1).

This study consists of a Screening Period, Baseline Period, Treatment Period, and Taper Period. The investigators will obtain informed consent at Visit 1 (Screening Visit). Subjects who are eligible for this study can enter the study. During the Screening Period, if subjects have previously taken medication such as COMT inhibitor and/or MAO-B inhibitor, they have to undergo an appropriate wash-out period for each medication before conducting Visit 2 (Baseline). During the Treatment Period, subjects will take the study drug daily for 18 weeks, and scheduled study visits will be Visit 3 and Visit 4 (18 weeks: EOT).

Subjects will complete their participation in the clinical trial after they complete Visit 4 (EOT). For subjects who require tapering at the time of Visit 4 (EOT), they will enter a Taper Period for 1 week. The Taper Period may be omitted if the subject's daily dose of the study drug at the end of treatment is 50mg, if subjects will continue to take the study drug after the completion of the trial, or if it is considered not required by an investigator.

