### 9.3.1 Inclusion Criteria

To be eligible for inclusion into this trial, the subjects must fulfill all of the following criteria:

1. Male or female, age  $\geq 19$  years at the time of informed consent
2. Patients who meet the clinical diagnostic criteria of Movement Disorder Society (MDS) diagnostic criteria 2015 for Parkinson's disease, have motor fluctuations with  $\geq 1.5$  hours of "off" time throughout the day which is confirmed at the time of Screening and take levodopa 3 or more times a day
3. Parkinson's Disease patients who are receiving levodopa without COMT inhibitor and/or MAO-B inhibitor

CCI

4. Be able to maintain an accurate and complete diary with the help of a caregiver as needed, recording "on" time, "on" time with dyskinesia, "off" time, and time asleep
5. Be able to provide written informed consent
6. Patients whose cognitive function, at the discretion of an investigator, is at a level appropriate to participate in the clinical trial (i.e., with a GDS score of 3 or less or a CDR of 0.5 or less within 3 months prior to Screening)

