#### **9.4.7.2 Prohibited Concomitant Medications and Therapies**

Prohibited concomitant medications and therapies are listed below.

Prohibited medications:

- Acetylcholinesterase inhibitors
- COMT inhibitor
- Any investigational drugs/biologics
- All the contraindicated medications listed on the approved label of study drug (Appendix 1)

Prohibited therapies:

- DBS(Deep brain stimulation)
- Surgical treatment
- LCIG(Levodopa-carbidopa intestinal gel) therapy

Concomitant medications and therapies listed above will be prohibited during the trial participation. Nevertheless, if continuous use of any prohibited medication/therapy is indicated for treatment of the subject during the trial, in the judgment of an investigator who treats the subject's other medical symptoms, the subject must discontinue the trial immediately, and the details should be recorded in the Case Report Form (CRF).

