## 9.5.2.2 Description of Procedures/Assessments Schedule

### 9.5.2.2.1 Visit 1 (Screening, -3 weeks ~ -1 day)

All procedures will be conducted after obtaining informed consent from subjects who want to participate in this clinical trial. After obtaining informed consent, the following procedures will be performed to establish eligibility for the trial:

- Demography
- Height
- Weight
- Medical history
- Prior and concomitant medications
- Concomitant therapies
- Clinical laboratory tests
- 12-lead ECG: if deemed necessary by an investigator based on subject's symptoms
- Vital signs
- Urine pregnancy test
- Physical examinations
- AE assessment
- Subjects and/or their caregivers receive a subject diary and investigator will train them how to complete a diary.
- Conduct the MMSE among the efficacy assessments.

During Screening Period, if subjects have previously taken medication such as COMT inhibitor and/or MAO-B inhibitor, they have to undergo an appropriate wash-out period for each medication.

Subjects who meet the eligibility criteria of the study will be instructed to complete the diary for 3 consecutive days prior to Visit 2 (Baseline).

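### MMSE takes its baseline at Screening, before the protocol's wash-outs, so in subjects who stop a drug after Visit 1 the 18-week change mixes that withdrawal with adding safinamide

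*Combined protocol and SAP*

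**What the plan says.** Table 3 schedules MMSE at Visit 1 and Visit 4 (and at premature discontinuation), with no entry at Visit 2. Footnote o states: "The result from MMSE conducted at Visit 1 (Screening) will be the baseline result". The same footnote and section 9.5.2.2.2 allow the test at Visit 2 if it was not done at Visit 1; that result then serves as baseline, and a test at either visit counts as MMSE completed.

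The other efficacy baselines are later. Section 9.5.2.2.2 places PDQ-39, MDS-UPDRS Parts 3 and 4 and KPPS at Visit 2. The baseline diary covers the days just before Visit 2.

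The wash-outs lie in between. Section 9.5.2.2.1 says: "During Screening Period, if subjects have previously taken medication such as COMT inhibitor and/or MAO-B inhibitor, they have to undergo an appropriate wash-out period". Section 9.1.1 gives the lengths ("3 days for COMT inhibitor; 14 days for MAO-B inhibitor"), and section 9.1 requires completion before Visit 2. Exclusion criterion 8 admits users of narcotic analgesics provided they consent to "at least 7 days of washout period prior to Visit 2, if known to take narcotic analgesics 7 days prior to Screening Visit".

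MMSE change is a secondary endpoint (section 9.7.1.1.2), analysed by a paired t-test on the week-18 change (section 9.7.1.7.2) at a two-sided 2.5% level (section 9.7.1). There is one arm.

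**The concern.** The study title describes safinamide added to levodopa. A change score answers that question only if its baseline is the state to which safinamide is added. For PDQ-39, MDS-UPDRS and KPPS it is: the subject reaches Visit 2 on levodopa with the listed drugs stopped. For MMSE the default baseline precedes that state whenever a drug is stopped after Visit 1. The change then covers two events, withdrawal of the old drug and addition of safinamide. For a subject coming off another MAO-B inhibitor it is closer to a switch, because section 7.1 describes safinamide as itself inhibiting MAO-B.

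With no control arm, any shift in MMSE caused by the withdrawal enters the mean change and would be read as part of the safinamide result. Within one subject, the MMSE and PDQ-39 changes would start from different treatment states.

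**Working it through.** **1. Order of events.** Inclusion criterion 3 asks for levodopa without a COMT or MAO-B inhibitor, which on its own could mean that these drugs are already gone at Visit 1. Sections 9.1 and 9.5.2.2.1 show otherwise: the wash-out takes place in the Screening Period, and eligibility is reconfirmed at Visit 2. Exclusion criterion 8 likewise counts the narcotic-analgesic wash-out back from Visit 2. The protocol thus provides for this sequence: MMSE on the old drug, drug stopped, Visit 2 baselines, safinamide from the next day.

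**2. Intervals.** Inputs: Visit 1 from -3 weeks to -1 day; Visit 4 at 18 ± 2 weeks, so weeks 16 to 20.

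- Scales with a Visit 2 baseline: 16 to 20 weeks.
- MMSE, shortest: 16 weeks + 1 day. Longest: 20 + 3 = 23 weeks.
- If the drug is stopped no earlier than the day of Visit 1, the wash-out length sets the minimum gap before Visit 2. After a MAO-B inhibitor (14 days) the MMSE interval is 16 + 2 = 18 to 23 weeks. After a narcotic analgesic (7 days) it is 16 + 1 = 17 to 23 weeks. After a COMT inhibitor (3 days) it is 16 weeks + 3 days to 23 weeks.

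**3. Who is affected.**

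| Subject | MMSE baseline | What the MMSE change contains |
|---|---|---|
| Stops no listed drug after Visit 1 | Visit 1, up to 3 weeks early | Safinamide period plus a short run-in |
| Stops a drug after Visit 1, MMSE done at Visit 1 | Before wash-out | Withdrawal plus safinamide |
| Stops a drug after Visit 1, MMSE done only at Visit 2 | After wash-out | Safinamide period |

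Rows two and three can both occur under footnote o, so the baseline state varies by which visit happened to include the test.

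**4. Size.** The protocol gives no planning figure for MMSE. Its stated sizes do reproduce: the exact paired t-test at two-sided 0.025 gives 31 for off time (power 0.9027) and 149 for PDQ-39 (power 0.9017), and 149/(1 - 0.25) = 198.67, rounded up to 199. None of these depends on the MMSE baseline.

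Let f be the share of subjects who stop a drug after a Visit 1 MMSE, and d the resulting shift in MMSE in standard deviations of the change score. The bias in the mean change is f × d. With no true safinamide effect, the paired t-test follows a noncentral t with noncentrality f × d × √n. The documents give neither f nor d, nor an MMSE standard deviation. The table shows the rejection rate against the nominal 0.025 for assumed values, taking n = 149 as a stand-in:

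| f | d = 0.1 | d = 0.2 | d = 0.3 | d = 0.5 |
|---|---|---|---|---|
| 10% | 0.026 | 0.029 | 0.035 | 0.053 |
| 25% | 0.032 | 0.053 | 0.092 | 0.233 |
| 50% | 0.053 | 0.152 | 0.335 | 0.784 |

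The range runs from negligible to large, and the bias is zero if f or d is zero. The test is two-sided, so the sign of d does not alter these rates. The table illustrates the mechanism; it does not estimate the bias in this trial.

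**The case against.** The strongest reply is that the effect may be nil. Only subjects who stop a drug between the two visits are confounded, their number is unknown, and the documents do not say that stopping these drugs moves MMSE. A single-arm study cannot firmly attribute MMSE change to safinamide anyway, and anticholinergics and amantadine may be adjusted throughout. Section 9.7.1 defers detail to an SAP whose text is not in the document reviewed, so handling at analysis cannot be ruled out. All of this stands. It limits the weight of the point but does not justify an avoidable extra source of change.

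A second reply is that MMSE has a role at Visit 1: section 9.5.2.2.1 lists it among the eligibility procedures, and it could inform the investigator's judgement of cognitive suitability. That stands in part. However, inclusion criterion 6 is framed by GDS or CDR ("with a GDS score of 3 or less or a CDR of 0.5 or less within 3 months prior to Screening"), no criterion uses an MMSE score, and footnote o lets the Visit 1 test be missed.

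A reader might infer more than the documents support:

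- **Acetylcholinesterase inhibitors as a further confounder.** Section 9.4.7.2 says "Concomitant medications and therapies listed above will be prohibited during the trial participation", and these drugs are on that list. But nothing describes subjects entering on them or a wash-out for them, the prohibition is not said to start only after Visit 1, and nearby criteria text is redacted.
- **All washed-out drugs being absent at week 18.** The prohibited list does not name narcotic analgesics or MAO-B inhibitors. They could be covered only through the label contraindications in Appendix 1, which is not in the text reviewed.
- **A known direction or a shift in MMSE points.** Neither is given for any of these drugs.

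**Conclusion.** The point holds, within limits. By default the MMSE baseline precedes the wash-outs. For subjects who stop a COMT inhibitor, MAO-B inhibitor or narcotic analgesic after Visit 1, the MMSE change is therefore not a comparison of levodopa with levodopa plus safinamide. For everyone else, the consequence is a baseline up to 3 weeks earlier than that of the other scales. The certain effects are a baseline state that differs between subjects and an interval of 16 weeks plus 1 day to 23 weeks in place of 16 to 20. The bias itself cannot be quantified in size or direction and may be zero. It would be wrong to conclude that the whole MMSE result is confounded, or that the trial's main conclusions are at risk: MMSE is one secondary endpoint, and the co-primary endpoints and sample size are unaffected. The case for acting rests on how cheap the correction is, not on a demonstrated large error.

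**What to change.** Reword footnote o, the MMSE row of Table 3, and sections 9.1.1, 9.5.2.2.1 and 9.5.2.2.2 so that the Visit 2 MMSE is the baseline for all subjects. If Visit 1 testing must stay, require a Visit 2 MMSE as baseline for any subject who stopped a COMT inhibitor, MAO-B inhibitor or narcotic analgesic after Visit 1.

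For data already collected, add to the SAP a sensitivity analysis of MMSE change by wash-out status and by visit of the baseline MMSE. The medication start and end dates needed are already recorded under section 9.4.7.

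The cost is small. Visit 2 becomes a few minutes longer, at a visit that already takes place and where the protocol already permits the test. MMSE is done twice before treatment where a site also wants it at screening to help judge cognitive suitability, or where a washed-out subject has already been tested at Visit 1.
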